10.3 Definition of Populations

Our population includes patients 18-65 y.o.a. who have tested positive with COVID-19 and are either asymptomatic but exposed in the prior 7 days or are symptomatic with symptom development in the prior 7 days. Inclusion and exclusion criteria (described elsewhere) will be met. We are not treating patients for SARS-CoV-2.

10.4 Study Stopping Rules

Analysis will occur at several points, while enrolling and collecting samples from 125 patients, in batches of 25 randomized participants. Analysis will occur after enrollment of 25, 50, 100 and then 125 participants and will include viral load and replication (as measured by changes in genomic, strand, and subgenomic expression and will be evaluated and compared between treatment groups). No interim analyses of data will be performed. mRNA obtained from salivary samples will be analyzed and will be assessed by RT-PCR at time points 0 and 30 min. Infectivity assays will be subsequently performed on salivary samples collected at time points 0 min ('baseline') and 30 min post rinse with cycle threshold of 22 or lower (CT22) as determined by RT-PCR using primers specific for SARS-CoV-2 viral products. If the cycle threshold is above 22 (CT22), samples are considered to contain insufficient virus for use in viral infectivity assays. This cycle threshold has been empirically determined by the [name] laboratory (personal communication, [name]).

If saliva samples from patients 6-7 days post-diagnosis are found to routinely have insufficient viral load at interim analysis (at n=25 or 50), the study will be modified for more stringent enrollment criteria (with inclusion up to 5 days post-diagnosis rather than 7, as salivary viral load diminishes with time after infection). Because all oral rinse products are commercially available, low risk products that have previously undergone extensive safety testing and approval procedures, we do not anticipate a situation where safety concerns to participants necessitates halting the study. Adverse events will be reported and reviewed by our internal quality control committee. Medical problems that occur in our facility will be reported as needed to the IRB board and emergency medical personnel will be contacted to care for the patient and potentially bring them to the adjacent UNC medical hospital. If a significant number of adverse events or reactions are witnessed (defined as more than 1 per 20 patients), a safety review will be triggered and study personnel will look at the records in an unblinded fashion to see if one mouthrinse is causing reactions. If that is the case, the mouthrinse study arm associated with adverse events will be discontinued, but the mouthrinse arms associated with minimal adverse events will continue.

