At the conclusion of sample collection, the participant will undergo a periodontal exam and will receive a \$50 gift card for their participation in visit 2. Study participation concludes following the periodontal exam after visit 2.

Missing data may occur due to participants being unable to complete a study visit due to health concerns or insufficient salivary production. Any missing data will be excluded from the study analysis. We do not anticipate that this will bias the data in any way. To accommodate this eventuality, we plan to enroll 30 participants per arm, to be able to have 25 participants per arm with full datasets.

All salivary samples will be collected on ice in sterile 50 mL conical vials and blood will be collected in EDTA-containing blood collection tubes. All collection tubes will be labelled “COVID Core” using pre-printed labels including the participants random alphanumeric study ID. Saliva samples will be cataloged and stored at the UNC Delta COVID Translational Initiative (also referred to as the COVID Core) for future RT-PCR, cytokine and chemokine concentration (Luminex) and viral infectivity assays. Samples will be transported on ice in a secondary container from the collection site to 4403A Koury Hall in leak proof biohazard bags. Samples will be processed according to the **sample processing and outcomes** procedure (below).

Participants who successfully provide salivary and blood samples and follow study protocols will receive a \$30 gift card as compensation at the end of visit 1 and \$50 at the end of visit 2. This study involves two, 90 minute on site visits.

During the period that the study participants are present in the clinic and giving saliva samples, we will monitor patient wellbeing and inquire about their comfort. If participants exhibit signs of distress or if oxygen saturation drops, research study staff will contact emergency medical responders to visit the patient and if deemed appropriate, the participants will be escorted to UNC hospital (adjacent building).

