4. SELECTION AND ENROLLMENT OF PARTICIPANTS

4.1 Inclusion Criteria

Subjects must meet all of the following inclusion criteria to be eligible for enrollment in the study:

- Diagnosed SARS-CoV-2+ status. Either became symptomatic in the prior 7 days, or if not symptomatic, likely infected/exposed within the prior 7 days. All patients listed from the UNC Respiratory Diagnostic Center (RDC) have a confirmed SARS-CoV-2 infection and have consented to be contacted for research purposes. For patients contacting study coordinators for enrollment, who were not tested in the RDC, they must provide written proof of positive SARS-CoV-2 status in the prior 7 days.
- Individuals (all sex, all gender) at least 18 y.o.a. and at most 65 y.o.a. and in good oral health without any known allergies to commercial dental products or cosmetics. ASA class I or II prior to SARS-CoV-2 infection.
- Evidence of a personally signed and dated informed consent document indicating the subject (or legally acceptable representative) has been informed of all pertinent aspects of the trial and all of their questions have been answered.
- Able to comprehend and follow the requirements of the study (including availability on scheduled visit dates) based on research site personnel’s assessment.

- Females of childbearing potential will have a negative urine pregnancy test (on site) or be physically incapable of pregnancy (implants or injections, Intrauterine device, Bilateral tubal ligation, Hysterectomy, Ovariectomy, Women post-menopausal)

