10.5 Outcomes

All oral rinse products are commercially available, low risk products. Therefore, adverse outcomes are anticipated to be extremely rare, and will be reviewed weekly by the study team/committee. Any adverse event will be documented in our CDART database system.

The primary and secondary outcomes of RT-PCR (RQ), viral infectivity (RF), and cytokine/chemokine analyte concentration (pg/mL) for each sample type and each participant will be stored as a comma-separated values file analyzed using Excel (or similar) software. This data will be available to research study personnel weeks to months after sample collection when the experiments are conducted. Samples will be run in batches resulting in large spreadsheets of data. Periodontal exam data will be entered into CDART and can be exported as a comma-separated values file.

The outcomes do not include patient treatment response, and therefore the outcomes will not be reviewed and adjudicated by an outside committee. The study personnel will constitute their own committee that meets weekly, and they will review and evaluate the data once these experiments are conducted. The committee will not be masked to the participant's group assignment; the statistician will conduct analyses and then the committee will evaluate the data to reach scientific conclusions on which mouthrinse is more effective.

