10.6 Data Analyses

qRT-PCR: Data will be presented as mean (standard deviation) for normally distributed data and as median [Interquartile range] for non-normally distributed data. P values will be reported as two tailed. Between group comparisons will be performed using a Student's T test or Mann-Whitney test. Normality will be assessed using the Kolmogorov-Smirnov test, and logistic regression will be performed with robust standard errors. Methods adapted from Bullard *et al* 2020.

Viral infectivity: The viral infectivity analysis will compare infectivity levels between mouth rinse types and across the time course for calculation of the reduction factor (RF). The RF will be calculated as the difference in the quotient of the infection titre before ('control titration') and after the mouthrinse ('remaining virus'). Therefore, the log₁₀ titre and its (double) standard deviation (SD) were calculated as well as the variance of the RF.

Inflammatory Markers: Inflammation-associated cytokine and chemokine concentrations (IL-6, CXCL-10, IL-8, and IL-10 [pg/mL]) will be quantified from saliva and blood samples collected at each visit and across the salivary collection time course using multiplex analyte analysis (Luminex technology) and using internal, manufacturer supplied standards of known concentration (pg/mL).

The analysis plan will include use of sensitivity analyses to evaluate the robustness/fragility of the study's main results to reasonable perturbations of the statistical methods and assumptions used in the main analysis. We will first describe the demographics (age, race, sex and BMI) for each study arm. If significant differences are found between groups, we will adjust the remainder of the analysis. The main analysis will be a repeated measures linear regression model(s). If multiple demographics are found to be significantly different the propensity scores will be created and final models will be adjusted by propensity scores. In the primary analysis, viral load and replication as measured by changes in genomic, strand, and subgenomic expression, will be evaluated and compared between treatment groups. Repeated measures linear regression models will be utilized to look at changes in viral load logarithmically before and after treatment. Similarly,

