in the secondary analyses, the repeated measures linear regression will be used to compare the changes in other continuous outcomes (such as immunological parameters) from baseline to specific time points outlined. Statistical significance will be tested using a two-sided 0.05 level with adjustments for multiple testing. Multiple testing correction will be made by Tukey adjustments (for multiple study arms) and False Discovery Rate (FDR) where appropriate (i.e. multiple inflammatory markers).

All statistical estimates of population parameters will be tabulated along with corresponding confidence intervals (CIs) and/or standard errors (SEs) to convey level of precision. All P- values will be reported as continuous numerical outputs (and not as dichotomous results). All hypothesis tests yielding large p-value (e.g., $p > \alpha$) will be reported as being inconclusive.

Power Calculation: Using data from Meiller *et al.* we calculated power at four time points.¹⁸ Time points included: Post-0 (immediately post rinse), Post-30 (30 min post rinse), and Post-60, (60 min post rinse). In addition, we calculated a Post-45, which was the midpoint between 30 and 60 min in the Meiller *et al.* data. Based on this viral study evaluating mouth rinse efficacy against infectivity of Herpes Simplex Virus, an enveloped virus, power calculations were determined to estimate effect size and determine sample size as a function of length of mouth rinse time course.¹⁸ The sample size was justified by a paired t-test on outcomes between time points. With three simultaneous comparisons (t_1-t_0 , t_2-t_1 , t_2-t_0) over 30 min, an $n=16$ sample size can detect the effect size in Cohen's $d=0.7$, which is between medium and large, with 80% power and 0.016 type-I error rate by Bonferroni correction. Therefore, with four simultaneous comparisons (t_0-t_1 , t_0-t_2 , t_0-t_3 , t_0-t_4) the sample size required for each arm is ~25 participants per group to discern oral rinse efficacy at any given time point (minutes post rinse).

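### Section 10.4 schedules by-arm comparisons at 25, 50, 100 and 125 participants, denies any interim analysis, then relies on one, and no rule covers repeated looks

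*Combined protocol and SAP*

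**What the plan says.** Section 10.4 makes three statements about analysis during enrolment:

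- "Analysis will occur after enrollment of 25, 50, 100 and then 125 participants and will include viral load and replication". The sentence goes on to say that these measures are compared between the treatment groups. It also describes batches of 25, which would imply a look at 75 that the list omits.
- "No interim analyses of data will be performed".
- If samples from patients 6–7 days after diagnosis "are found to routinely have insufficient viral load at interim analysis (at n=25 or 50"), the enrolment window is narrowed from 7 to 5 days after diagnosis.

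Section 10.6 describes the main comparison in almost the same terms: "In the primary analysis, viral load and replication as measured by changes in genomic, strand, and subgenomic expression" are compared between treatment groups. It sets a two-sided 0.05 level and adds "Multiple testing correction will be made by Tukey adjustments (for multiple study arms) and False Discovery Rate (FDR) where appropriate", giving multiple inflammatory markers as the FDR case.

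Section 10.5 says of the study-personnel committee that evaluates the data: "The committee will not be masked to the" participants' allocation.

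**The concern.** A reader cannot tell whether the early batches are arm-blind checks that saliva holds enough virus, or efficacy analyses by arm. The two have different consequences.

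If they are efficacy analyses and any of them could support a conclusion, the chance of a false claim is well above the stated 5%. If only the last analysis supports conclusions, its error rate is intact. By-arm results could still be known to study personnel when the enrolment window is changed, or when the main model is settled. That model is open: the Primary Outcomes text in section 10 calls ANCOVA on infectivity the primary analysis, while section 10.6 calls repeated-measures regression the main analysis and places viral load in the primary analysis.

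The only decision tied to the looks is whether later samples contain enough virus. It needs no treatment labels.

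**Working it through.** **1. The statements side by side (section 10.4)**

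| Statement | Implication |
|---|---|
| Analysis at 25, 50, 100, 125, compared by arm | Three by-arm looks before the last |
| No interim analyses | No looks before the last |
| Enrolment change on an interim analysis at n=25 or 50 | At least one look before the last |

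The first and third each contradict the second.

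**2. What the stated adjustments cover**

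- Tukey: several arms (10.6).
- FDR: several inflammatory markers (10.6).
- Bonferroni 0.016: comparisons between saliva time points, in the sample-size text (2.2, 10.2, 10.6).
- Repeated looks: nothing. There is no boundary, no spending rule, and no statement that early looks are descriptive or that only the last test is confirmatory.

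**3. The plan's own figures**

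Five arms × 25 = 125, the last listed look. The 25 per arm comes from a paired t-test with d = 0.7 and four comparisons. At two-sided 0.05/4 = 0.0125 the exact calculation gives n = 26 for 80% power (78.0% at n = 25), close to the stated figure. No overall error rate across looks is stated, so there is none to reproduce.

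**4. Type I error if p<0.05 at any look counts**

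Assumptions: equal arms at each look (block size is not given), no true difference, each look tested at unadjusted two-sided 0.05. For one contrast the standardised statistics are jointly normal with corr(Z_j, Z_k) = √(N_j/N_k):

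- 25 with 50: √0.5 = 0.707; 25 with 100: √0.25 = 0.5; 25 with 125: √0.2 = 0.447
- 50 with 100: 0.707; 50 with 125: √0.4 = 0.632; 100 with 125: √0.8 = 0.894

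Type I error = 1 − P(|Z_k| < 1.96 at every look). The t and Tukey columns come from 200,000 simulated five-arm trials with 5, 10, 20, 25 (or 30) per arm.

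| Looks | One contrast, normal | One contrast, t | Any pair, Tukey at each look |
|---|---|---|---|
| 25, 50, 100, 125 | 13.1% | 13.5% | 14.0% |
| 25, 50, 100, 150 | 13.6% | 14.0% | 14.5% |
| 25, 50, 100, 125, 150 | 14.5% | 14.9% | 15.7% |
| 125 only | 5.0% | 5.1% | 5.0% |

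The rows ending at 150 are there because section 3 says "we plan to enroll 30 participants per arm, to be able to have 25 participants per arm with full datasets", and 5 × 30 = 150. Adding the omitted look at 75 to the first row gives 14.2% for one contrast.

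To hold 5% for one contrast over 25/50/100/125, a constant boundary needs nominal p of about 0.0176 at each look. An O'Brien-Fleming-type boundary needs about 0.000006, 0.0014, 0.0235 and 0.043.

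**5. What an early by-arm look could show**

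The plan gives no between-arm effect size, so its paired d = 0.7 is borrowed here as an assumption. Two-sample t-test, two-sided 0.05, noncentrality d√(n/2):

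- n = 5 per arm: 0.7 × √2.5 = 1.107, critical t (8 df) 2.306, power 16.5%
- n = 10 per arm: 0.7 × √5 = 1.565, critical t (18 df) 2.101, power 31.7%

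By-arm looks at 25 and 50 participants would therefore carry little information even if wanted.

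**The case against.** The strongest reply is that the inflation depends on a rule the plan does not contain. Nothing permits an early efficacy claim or stop. The only stated consequence of an early look is a narrower enrolment window, applied to all arms alike. The denial of interim analyses supports reading the looks as virus-sufficiency checks, and on that reading the error rate is 5.0%. This stands, and it is why the 13–14% is conditional. It does not explain why the looks are described as comparisons between arms.

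Other text also helps the plan:

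- Section 10.6 reports p-values on a continuous scale and calls large ones inconclusive. It also sets a 0.05 level, so this is not decisive.
- The Primary Outcomes text says the linear model is specified a priori. The plan then names two different main models, which undercuts that.
- Section 10.5 says data arrive weeks to months after collection, so early looks may be late. Late by-arm results are still by-arm results.
- The main objective is infectivity, whereas the looks name viral load. That narrows the point, but viral load is also listed as a primary outcome.
- No section says each look goes to the unmasked committee. That is correct; equally, no section withholds by-arm results from it.

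Concealed envelopes and blinded sample collection and laboratory work (6.2.2, 6.2.3) do limit operational bias. They do not cover those who evaluate the data.

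**Conclusion.** Section 10.4 is wrong as written. The contradiction lies in the text and rests on no assumption. It should be resolved before the analysis plan is relied on.

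The size depends on a point the plan leaves open. If a nominal p<0.05 at any of the four looks could support a claim, type I error is 13.1% for one contrast (13.5% with a t-test) and 14.0% for any pair under Tukey, assuming equal arms. It is somewhat higher if recruitment runs to 150. If claims rest only on the final analysis, it is 5.0%, and the remaining risk is that by-arm results are known while the enrolment window or the main model is still being decided.

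**What to change.** - State that there is one between-arm efficacy analysis, after the last participant. Reconcile the total of 125 with 30 per arm.
- Remove the by-arm comparison from the earlier looks, and remove the sentence that conflicts with the n=25/50 check.
- Limit the n=25 and n=50 looks to pre-rinse cycle threshold, pooled over arms with labels withheld: the share of samples at 22 or lower, by days after diagnosis. Make this the sole basis for the enrolment-window decision already in 10.4. Pre-rinse matches the definition of baseline in the abbreviations table and section 6.2.2. Section 3 uses time 0 for the first post-rinse sample, so name the sample explicitly.
- Reconcile the day count in 10.4, which runs from diagnosis, with section 4.1 ("Either became symptomatic in the prior 7 days, or if not symptomatic, likely infected/exposed within the prior 7 days") and with the 48-hour diagnosis limit in the eligibility summary table.
- If by-arm looks are wanted, specify an alpha-spending boundary (for example O'Brien-Fleming type) and keep recruiting and sample-collecting staff blind to the efficacy results.

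The adverse-event review in 10.4 is separate and unaffected.

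Cost: a wording change, plus the IRB review that section 12.1 requires for any modification. The check on viral load is kept. The team gives up seeing efficacy results by arm before the end.

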After the participant expectorates the mouth rinse, research staff will collect another salivary sample (T_0 , 2 mL over 5 min). During a 10 min recuperation period, the study participants will answer demographics survey questions and questions regarding the taste, color, flavor and general acceptability of using the mouthrinse as part of routine dental and medical visits. At 15 minutes post-rinse, the participant will be asked to provide an additional saliva sample (2 mL over 5 min), followed by another 10-minute recuperation period. This sequence will be repeated for the 30, 45- and 60-minute time points post-rinse. At 60 minutes, the study participant will give their final salivary sample (2 mL over 5 min).

The samples will be stored and used for determining SARS-CoV-2 viral load by RT-PCR and inflammation-associated cytokine and chemokine concentration (pg/mL). The impact of mouthrinses on viral load in samples will be using a Relative quantification (RQ) ratio. A cycle threshold cut off (see sections 9.4-9.5) of 22 will be used for determining which samples will be used in downstream viral infectivity assays. Viral infectivity will be calculated (see sections 9.4-9.5) and yield a Reduction Factor as quantified output. Peripheral blood will be collected at the end of salivary collection (2 - 5 mL in EDTA-containing blood collection tubes).

Participants will be provided materials and oral hygiene instruction related to daily use of oral hygiene products provided by the study. During the week between study visits, participants will be directed to brush with Colgate toothpaste (at least twice per day) and rinse with the Colgate mouthrinse according to on-label instructions (10-20 mL, 30-60 seconds, 2-3 times per day depending on mouthrinse).

Participants will be asked to keep a daily diary of oral hygiene performance, product usage, COVID-19 symptoms and exposures. Participants will be given a \$30 gift card for their participation in visit 1. Participants will be scheduled to return to the GoHealth Clinical Research Unit at one week after the baseline assessment, during which additional salivary (1 time point, 2 mL

of saliva over 5 min, no rinse will occur) and blood samples (2 - 5 mL in EDTA-containing blood collection tubes) will be collected.

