10.2 Research Hypotheses

The central hypothesis of this study is that COVID-19+ patients will have a >20% reduction in SARS-CoV-2 viral infectivity following oral rinse with an antiseptic mouthrinse and that this reduction will persist for at least 30 minutes.

The secondary hypothesis is that COVID-19+ patients using Colgate oral health products will have lower inflammatory marker levels than controls. Furthermore, we hypothesize that COVID-19+ patients will have a greater incidence of periodontal disease than the general population.

Sample Size Considerations

Using data from Meiller *et al.* we calculated power at four time points.¹⁸ Time points included: Post-0 immediately after rinse, Post-30 (30 min post rinse), and Post-60 (60 min post rinse). In addition, we calculated a Post-45, the midpoint between 30 and 60 min, in the Meiller *et al.* data. Based on this viral study evaluating mouth rinse efficacy against viral infectivity of Herpes Simplex Virus, an enveloped virus, power calculations were determined to estimate effect size and determine sample size as a function of length of mouth rinse time course.¹⁸ The sample size was justified by a paired T-test on outcomes between time points. With three simultaneous comparisons (t_1-t_0 , t_2-t_0 , t_2-t_1) over 30 min, an $n=16$ sample size can detect the effect size in Cohen's $d=0.7$, which is between medium and large, with 80% power and 0.016 type-I error rate by Bonferroni correction. Therefore, with four simultaneous comparisons (t_1-t_0 , t_2-t_0 , t_2-t_1 , t_3-t_0) the sample size required for each arm is ~25 participants per group to discern oral rinse efficacy at any given time point (minutes post rinse).

Statistical analysis of our data will be performed by [name], the statistician on this project. Statistical analysis of our data will be performed by [name], the statistician on this project. [name] will be involved in all stages of this project to help ensure statistical rigor.

Primary Outcomes

The analyses will compare viral titre (RT-PCR) and viral infectivity levels between mouth rinse types and across the time course.

Table: Variable Types for Primary Outcomes

	Viral Infectivity (Continuous)	Viral Load (Continuous)
Age, Years (Continuous)		
Race (Categorical)		
Sex (Categorical)		
BMI (Continuous)		
Time (Categorical)		
StudyGroup (Categorical)		

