10.5.1 Primary Outcome

The primary objective of this study is to determine the efficacy of antiseptic mouthwashes on reducing SARS-CoV-2 cellular infectivity in participant saliva. *We hypothesize that COVID-19+ patients will have a >20% reduction in SARS-CoV-2 viral infectivity following a 60 second oral rinse with an antiseptic mouthrinse and that this reduction will persist for at least 30 minutes.* This primary objective will focus on quantifying SARS-CoV-2 viral infectivity and mRNA level using an *in vitro* infectivity assay (Reduction factor (RF) calculated from PFU/mL) and RT-PCR (relative quantification [RQ] ratio). This objective provides urgently needed data to guide healthcare workers on the proper use of specific commercially available mouthwashes capable of reducing SARS-CoV-2 viral infectivity and potentially limiting COVID-19+ transmission.

Outcome assessments will be conducted weeks to months after the study visit, when RT-PCR and viral infectivity assays are routinely conducted in the COVID Core and the laboratory of [name], respectively.

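### Screening 30-minute post-rinse samples at CT 22 makes entry to the primary infectivity analysis depend on a post-randomisation outcome; the between-arm comparison may be biased and pairs are lost

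*Combined protocol and SAP*

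**What the plan says.** Section 3 (Study Design) sets a cut-off that works sample by sample: a cycle threshold "of 22 will be used for determining which samples will be used in downstream viral infectivity assays". Section 10.4 repeats it and names the samples concerned, those at 0 min (labelled baseline) "and 30 min post rinse with cycle threshold of 22 or lower (CT22". It adds: "If the cycle threshold is above 22 (CT22), samples are considered to contain insufficient virus for use in viral infectivity assays". Neither section limits the rule to pre-rinse samples. Thirty minutes is the time point in the primary hypothesis (sections 1.1, 10.2 and 10.5.1).

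The RF is defined in the abbreviations table as log10 of pre-rinse load over post-rinse load, so it needs an assayed post-rinse titre. The only missing-data rule is in section 3: "Any missing data will be excluded from the study analysis", followed by "We do not anticipate that this will bias the data in any way". The causes given there are inability to complete a visit and low saliva production; CT failure is not mentioned.

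RNA level is itself a primary outcome. Under Primary Outcomes in section 10: "The analyses will compare viral titre (RT-PCR) and viral infectivity levels between mouth rinse types and across the time course". Section 10.5.1: "This primary objective will focus on quantifying SARS-CoV-2 viral infectivity and mRNA level".

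Two places read differently. The plaque-assay paragraph under Sample processing and outcomes (section 3) and section 11.3.3 both say that all samples are diluted or run, with no mention of a CT screen.

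**The concern.** A high post-rinse CT means little viral RNA after the rinse, which is the direction of benefit. Under the CT rule, someone with pre-rinse CT 20 and 30-minute CT 24 has no post-rinse titre, hence no RF, and is excluded. Those lost tend to have a large RNA fall or a pre-rinse CT already near 22.

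If RNA falls more on an active rinse than on water, the arms lose different shares of their pairs. If a large RNA fall also goes with a large infectivity fall, the active arm loses more of its best responders and the comparison moves towards the null. The plan's statement that exclusion causes no bias has no argument behind it. The >20% hypothesis is worded as a reduction within patients, so the within-arm estimate matters too.

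**Working it through.** **1. The plan's own figure.** Paired t-test, d = 0.7, two-sided alpha 0.05/4 = 0.0125, 80% power: the noncentral t gives n = 26 and the normal approximation 23, so the stated ~25 per arm reproduces. Power at n = 25 is 78%. This counts participants with usable pairs and makes no allowance for CT failure.

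**2. What the documents do not give.** There is no CT distribution, no RNA effect of any rinse, and no correlation between RNA and infectivity reductions. All are assumed here: pre-rinse CT normal with mean 20, 22 or 24 and SD 4; 3.32 cycles per log10; SD of each reduction 0.5 log10; correlation 0.7 unless stated.

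**3. The rule as simulated.** A pair enters if pre-rinse CT ≤ 22 and pre-rinse CT + 3.32 × (RNA reduction in log10) ≤ 22. The result is mean RF in the active arm minus mean RF in the water arm.

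**4. RNA falls as much as infectivity** (1.0 log10 active, 0.2 water; true difference 0.80):

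| Mean pre-rinse CT | 20 | 22 | 24 |
|---|---|---|---|
| Eligible pairs kept, active | 55% | 44% | 35% |
| Eligible pairs kept, water | 86% | 81% | 76% |
| Observed RF difference | 0.73 | 0.71 | 0.69 |

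The planned models do not remove this. ANCOVA on pre-rinse titre, or an unstructured repeated-measures model, gives 0.62 to 0.72, because post-rinse RNA drives the missingness and is not in the infectivity model. Section 10.6 states "The main analysis will be a repeated measures linear regression model(s", so this applies to the main analysis.

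**5. Dependence on the two conditions** (mean RF difference, true 0.80, over the three CT means):

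- correlation 0.3: 0.75 to 0.77
- correlation 0.5: 0.72 to 0.75
- correlation 0: 0.80, no bias
- correlation -0.3: 0.83 to 0.85, bias reversed
- RNA falling half as much (0.6 against 0.2), correlation 0.7: 0.74 to 0.76
- equal RNA change in both arms, correlation 0.7: 0.80 and equal retention, but a true within-arm 1.0 reads 0.89 to 0.94

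**6. The plan's 20% threshold.** A 20% reduction is RF = log10(1/0.8) = 0.097. Within one arm at correlation 0.7, it reads about 10, 5 and 1% at mean CT 20, 22 and 24 if RNA falls equally, and about 12, 8 and 4% if RNA is unchanged. At correlation 0 it reads 20%.

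**7. Power, by source of loss.** The pre-rinse screen passes 69, 50 and 31% of 25, or about 17, 12 and 8. Paired power at d = 0.7 and alpha 0.0125 falls from 78% to 54, 34 and 18%. Taking d = 0.7 as 0.35 log10 over SD 0.5, with RNA falling equally, the post-rinse screen leaves about 14, 9 and 5 pairs. Power is then 27, 11 and 4% at correlation 0.7 (observed d 0.57, 0.52 and 0.46), or 43, 22 and 8% at correlation 0. Only this second drop comes from screening the post-rinse sample.

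**8. The remedy.** Screening the pre-rinse sample only, with all post-rinse titres observed, returns 0.80. With a detection limit placed at the equivalent of CT 22 (an assumption), 45 to 62% of eligible active-arm titres in the step 4 case fall below it. A censored-likelihood model then returns about 0.79 to 0.82. Substituting the limit gives 0.44 to 0.57, worse than exclusion.

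**The case against.** The strongest reply is that the CT rule may not govern. If the all-samples wording in the plaque-assay paragraph and section 11.3.3 prevails, nothing is selected. That conflict is central. Still, those are general processing and quality statements, while sections 3 and 10.4 give an explicit selection rule; the documents do not say which prevails.

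Second, the bias needs two facts that the documents do not supply. The membrane-disruption mechanism in sections 2.1 and 2.2 is compatible with inactivation without a greater fall in RNA. This stands: a reader might infer that the planned comparison is biased towards the null, and the documents support only that it may be.

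Third, a reader might infer that the primary outcome is left undefined for failed samples. That goes too far: the section 3 exclusion rule refers to any missing data and can cover them. The fault is that this rule selects on an outcome.

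Fourth, section 10.4 would tighten enrolment if viral load proves too low. Higher pre-rinse load would also reduce post-rinse failures (active retention rises from 35% to 55% as mean CT goes from 24 to 20), but it does not make failures equal across arms.

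Fifth, section 10.4's 0-min label might suggest that both screened samples are post-rinse, since sections 3 and 5.1 use time 0 for the first post-rinse sample. The abbreviations table and section 6.2.2 define baseline as pre-rinse, so this is only a labelling mismatch.

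**Conclusion.** The concern holds conditionally. Under the explicit CT rule, entry to the primary infectivity analysis depends on post-rinse RNA, a post-randomisation primary outcome, and the plan's claim that exclusion will not bias the data is unsupported. Attenuation of the between-arm RF difference requires both a larger RNA fall on the rinse than on water and a positive within-person correlation. Its size is unknown; the 0.69 to 0.73 against a true 0.80 is an illustration under assumed values. With equal RNA change or zero correlation there is no between-arm bias, and with negative correlation the difference is overstated. Pairs are lost in every case.

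The whole fall in power should not be charged to the post-rinse screen: the part due to the pre-rinse screen remains after the fix.

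**What to change.** In sections 3 and 10.4:

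- Apply CT 22 to the pre-rinse sample only, and define the infectivity set as randomised participants with pre-rinse CT of 22 or lower.
- Plate their post-rinse samples at the planned time points whatever their CT.
- Analyse log10 titre, adjusted for pre-rinse titre, with a censored-likelihood (Tobit-type) model that treats plaque-negative samples as left-censored at the assay's detection limit. Do not substitute the limit.
- Report counts above CT 22 by arm and time point.
- If the laboratory cannot plate samples above CT 22, treat them as censored under a rule stated in advance, with a bounding analysis: post-rinse titre set to the pre-rinse titre, then to the detection limit.

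Reconcile sections 3 and 10.4 with the all-samples wording in the plaque-assay paragraph and section 11.3.3, and use one time-0 label throughout. Restate power for the number expected to pass the pre-rinse screen; the allowance of 30 enrolled for 25 complete does not mention CT failure. Settle this before arm-level results are seen, since section 10.4 plans group comparisons from the first 25 participants.

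The cost is wording plus plaque assays on samples already collected. Under the assumptions above, that is about 9 to 34 extra 30-minute samples across the trial at 25 per arm, each with replicates, and more if other time points are plated. For example, in the step 4 case at mean CT 22, with 12.5 eligible per arm: 12.5 × (4 × 0.56 + 0.19) ≈ 30. The stated power will be lower than 80%.
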